6.4 Summary table

	Baseline prior to entry	At 6 weeks after the last day of irradiation	Follow-up at 6 months after entry	Follow-up at month 12 and then yearly
Histological diagnosis	X			
MRI brain study (Gd+)	X	NO	X	△
Medical history	X	X	X	△
Physical examination	X	X	*	*
Performance Status	X	X	X	△
Concomitant medication	X	X	X	△
Mini-mental status	X	X	X	△
Adverse events scoring (CTCAE v.3.0)	X (acute)	X (acute)	X (late)	△ (late)
Survival		X	X	X

X Mandatory

* Recommended

△ Until tumor progression

7 Criteria of evaluation

7.1 Tumor progression

The maximum diameters in millimetres will be measured in three perpendicular directions. From this the volume can be calculated by the formula $1/6 \times 3,14 \times \text{length} \times \text{width} \times \text{height}$.

Attributing to possible inaccuracy of volume measurement is the difficulty to delineate the visible extensions due to the gradual transition of tumor into dural hyperaemia. Only clear dural thickening at the distinction of the investigator is to be considered tumor. Merely after a 25% increase of the calculated 3D-volume a decisive event is registered. This volume increase - or tumor recurrence in post-MRI Stage 3 disease - must at least exceed 0.065 cc (this is the volume of a 5mm-diameter sphere) in order to prevent valuation of subtle and possibly false positive tumor growth, as a consequence of 2-3 mm slice thickness and observer bias.

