
Treatment
 
Test product, dose and mode of administration
	
The treatment dose will be determined in function of the Simpson's stage.
 
Irrespective of WHO tumor grade patients with Simpson stage 1-3 will receive 60 Gy to the CTV1 and those with Simpson stage 4-5 will be treated with 60 Gy to CTV1 followed by a 10 Gy boost to the CTV2 (total, 70 Gy).
 
Volumes and prescribed dose should be according to the ICRU-50 report.
 
 ◆ GTV: postoperative tumor residual (CT or MRI). ◆ CTV1: GTV and/or subclinical microscopic tumor (may include the pre-operative tumor bed, peritumoral edema, hyperostotic changes if any, and dural enhancement or thickening as seen in the CT/MRI at diagnosis) + 10 mm or less, see dose constraints below. ◆ CTV2: GTV + 5 mm margin or less (see dose constraints, below). ◆ PTV1 & PTV2: CTV1 & CTV2 + 5mm margin (3 mm for stereotactic irradiation). These volumes needed to cover the CTV1 & CTV2 with the 95% isodose line, respectively. 
Fractionation: 2 Gy daily fractions, 5 fractions a week
 
Radiation quality: photon (> 4 MV) beams either conformal, stereotactic, or intensity-modulated radiation therapy (IMRT).
 
Dose constraints (total dose):
 
 ◆ optic pathways: 56 Gy (average); 60 Gy (maximum). ◆ Pituitary gland: 56 Gy. ◆ Brainstem: central, 54 Gy; surface, 64 Gy.
Duration of treatment	The treatment duration is therefore 6 weeks for Simpson's stage 1-3 and 7 weeks for Simpson's stage 4-5.
Reference therapy, dose and mode of administration	Not applicable

Criteria for evaluation
 
Efficacy
 
Safety
	
The primary trial endpoint is the 3-year progression-free survival rate in each stratum of the phase II study.
 
Progression-free survival is counted from entry on study until the first event of either death or progression (as demonstrated by an MRI showing either appearance of new lesions or increased in tumor size by 25% using 3 dimensions)
 
Overall survival is a secondary endpoint and is measured from date of entry to date of death, irrespective of the cause.
 
For both endpoints, the patients not having experienced the event(s) of interest are censored at the date of most recent follow-up.
 
Acute and long term toxicity will be scored according to the NCI-CTCAE version 3.0.
 
Neurological function will be measured by the Mini-Mental Status Evaluation.

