2.2 End-points

The primary trial endpoint is progression-free survival where progression is defined on the basis of tumor growth or appearance of new lesions (see chapter 7 for exact definition).

The secondary trial endpoints are acute and late effects classified according to the National Cancer Institute Common Terminology Criteria for Adverse Events v 3.0 (NCI CTCAE v3.0), mini-mental status (MMSE) and overall survival.

Quality of life is not an endpoint in this study since the trial is not randomized and is of relatively small size.

3 Patient selection criteria

Patients will be registered between surgery and the start of radiotherapy without exceeding 6 weeks time interval.

- ◆ **Histologically proven newly diagnosed atypical grade WHO grade II meningioma** (≥ 4 mitosis per high-power field [HPF] or the presence of at least 3 of the latter 4 variables: cellularity, architectural sheeting (i.e. patternless pattern), macronuclei and small cell formation) (see section 3.2 below for definition)

OR

- ◆ **Histologically proven newly diagnosed malignant WHO grade-III meningioma** (see section 3.2 below for definition)

(as assessed by the local pathologist)

AND all of:

- ◆ Complete or subtotal resection as assessed by the surgeon after verification with a postoperative MRI and according to Simpson guidelines (see section 3.4 below for definition). The patients will be stratified according to the resection status: complete excision (Simpson's stages 1-3) versus incomplete excision (Simpson's stages 4-5)
- ◆ Age between 18 years and 70 years
- ◆ WHO performance status 0-2
- ◆ All locations except optic nerve sheath tumors
- ◆ No neurofibromatosis type II patients (NF-2)
- ◆ No previous radiotherapy to the brain or meninges interfering with the protocol treatment plan
- ◆ No clinical evidence of second malignancies, except a history of cervix carcinoma in situ and basocellular carcinoma
- ◆ Women of reproductive potential must use effective contraception for the whole duration of the treatment and must not be pregnant or lactating.
- ◆ Absence of any psychological, familial, sociological or geographical condition potentially hampering compliance with the study protocol and follow-up schedule; those conditions should be discussed with the patient before registration in the trial
- ◆ Before patient registration, written informed consent must be given according to ICH/GCP, and national/local regulations.

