3.2 Simpson's guidelines for assessing resection level

The resection level will be assessed by the surgeon after verification with a postoperative MRI and will be classified according to Simpson guidelines as

Table 2. Simpson grading

Radical

Stage 1 : complete excision, including dura and bone.

Stage 2 : complete excision + supposed reliable coagulation of dural attachment.

Non-radical

Stage 3 : complete excision but insufficient dural coagulation or bone excision (non visible on MR, according to surgeon's opinion).

Stage 4 : incomplete excision, macroscopic rest visible (on MRI).

Stage 5 : biopsy only (visible on MRI).

4 Trial Design

For patients with atypical meningioma (grade II) the trial is designed as two parallel non-randomized phase-II trials with progression-free survival rate at 3-years as primary endpoint, in respectively patients with Simpson's stage 1-3 resection and patients with Simpson's stage 4-5 resection.

A separate one-stage Fleming design will be applied each to the two strata of patients. The criteria for success are respectively to demonstrate that the 3-year progression free survival is superior to 70% for patients with Simpson's stage 1-3 and that it is superior to 50% for patients with Simpson's stage 4-5.

With such a design, a total of 25 patients with Simpson stage 1-3 grade II meningiomas and 39 patients with Simpson stage 4-5 meningiomas are needed (total phase II study, 64 patients).

[figure not shown]
For the grade III meningiomas, given the small numbers expected to enter the trial, the patients will be registered only and treated and then followed-up similarly to the grade II meningiomas (see chapter 6). No specific statistical design, decision rule, or sample size is defined for this small group and only descriptive statistics will be produced.

The trial duration will be driven by the phase II study. It is foreseen that 6-13 grade-III patients will be registered during the accrual period of the phase II.

Patients need to be eligible and to have started treatment. The local pathology will be used for assessing eligibility.

Accrual to the phase II is anticipated to last 3 years.

Trial scheme:

5 Therapeutic regimens, expected toxicity, dose modifications

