5.1.3 Treatment planning

Treatment planning CT as well as a post-operative MRI scans are mandatory for (volume-based) 3D treatment plans (3D CRT, IMRT and SRT). Treatment portals will be defined by virtual simulation.

Fusion between the treatment planning CT and the post-operative MRI as obtained shortly before the registration is strongly recommended (see Definition of target volumes, chapter 1.5).

Multi-leaf collimators or secondary collimation with shielding blocks are mandatory in order to ideally conform to the PTV.

Treatment planning should conform to ICRU 50/62 rules for coverage of GTV, CTV and PTV (Ref. 89). Additionally, organs at risk (OAR) should be delineated according to the ICRU 62 rules: brain stem, optic chiasm, both optic nerves, pituitary gland, both eyes and both inner ears (cochleae), whenever appropriate depending on the location of the primary tumor.

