6.1 Before treatment start

The following evaluations have to be done:

- ◆ Local histology certifying meningioma WHO grade II or III. Mitotic index and if possible, MIB-1 index and, in women the progesterone/estrogen receptor status.
- ◆ Contrast enhanced pre and post-operative MRI in at least 2 plans. The post-operative MRI brain study should be done within 48 hours of the operation.

- ◆ Complete medical history including medications
- ◆ Physical examination including the performance scale evaluation (WHO performance scales see Appendix B)
- ◆ Mini-Mental Status Examination (MMSE, see Appendix F)

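### Section 7.1, to which section 2.2 defers for the exact definition of progression, omits new lesions and recurrence after Simpson stage 1-2, so the definitions of the primary endpoint conflict

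*Protocol*

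**What the plan says.** The primary endpoint is 3-year progression-free survival, so the definition of progression decides what is counted. The protocol gives it in three places.

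- Section 2.2: "progression is defined on the basis of tumor growth or appearance of new lesions (see chapter 7 for exact definition".
- Protocol summary, criteria for evaluation: "as demonstrated by an MRI showing either appearance of new lesions or increased in tumor size by 25% using 3 dimensions".
- Section 7.1: "Merely after a 25% increase of the calculated 3D-volume a decisive event is registered". The next sentence sets a minimum size: "This volume increase - or tumor recurrence in post-MRI Stage 3 disease - must at least exceed 0.065 cc".

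Nothing else in chapter 7 defines progression. Sections 7.2 and 8.2.1.1 use the word without defining it.

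Section 3.2 classes the first three Simpson stages as complete excisions, including "Stage 1 : complete excision, including dura and bone" and "Stage 2 : complete excision + supposed reliable coagulation of dural attachment". Section 5.1.2 treats Simpson 1-3 as having no visible tumor. All three stages form one stratum of the primary analysis.

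**The concern.** The text named as exact is narrower than the two texts around it. Three things are left open.

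1. New lesions are events in 2.2 and the summary but do not appear in 7.1, for any stage.
2. After stage 1 or 2 there is no baseline volume, so a 25% increase cannot be computed. Section 7.1 meets this difficulty by naming recurrence, but only for Stage 3.
3. Section 7.1 does not say which MRI the 25% increase is measured against.

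A site working from the summary and a site working from 7.1 could record different events for the same scan. The error has one direction: an uncounted recurrence raises the estimated 3-year PFS. In stratum 1-3, one reclassified patient can reverse the conclusion.

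**Working it through.** **Inputs.** Stratum 1-3: N = 25, P0 = 0.70, P1 = 0.90, type I error 0.09, type II error 0.098 (section 8.1.1.1). Success requires the one-sided 90% lower bound of the Kaplan-Meier estimate, log-log transform, to exceed 70%. The share f of stage 1-2 patients within the stratum is not given, so 25%, 50% and 75% are assumed. The share d of failures that are deaths is also not given, so 0 and 25% are assumed.

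**Step 1: reproduce the plan's figures.** Without censoring, S = x/25, the Greenwood standard error relative to S is √[(1−S)/(25S)], and the lower bound is S^exp(1.2816 × that error / |ln S|).

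- x = 21: S = 0.84, relative error 0.0873, bound 0.84^1.900 = 0.718, which passes.
- x = 20: S = 0.80, relative error 0.1000, bound 0.80^1.776 = 0.673, which fails.

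The rule is therefore at least 21 of 25 progression-free. P(X ≥ 21 | 25, 0.70) = 0.0905 and P(X ≤ 20 | 25, 0.90) = 0.0980, which match the stated error rates. The minimum volume also reproduces: 3.14/6 × 0.5³ = 0.0654 cc.

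**Step 2: apply 7.1 literally and alone.** At P0 the true failure proportion is 0.30. If imaging recurrences in the stage 1-2 share are not counted and only deaths are, then

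apparent PFS = 1 − 0.30 × [(1 − f) + f × d].

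The chance of false success is P(X ≥ 21 | 25, apparent PFS).

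| Assumed f | Apparent PFS, d = 0 | False success | Apparent PFS, d = 25% | False success |
|---|---|---|---|---|
| 25% | 0.775 | 0.31 | 0.756 | 0.23 |
| 50% | 0.850 | 0.68 | 0.8125 | 0.48 |
| 75% | 0.925 | 0.96 | 0.869 | 0.78 |

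For f = 50% and d = 25%: 1 − 0.30 × (0.50 + 0.125) = 1 − 0.1875 = 0.8125.

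**Step 3: apply 2.2 and the summary.** If new lesions and every recurrence after Simpson 1-3 count, apparent PFS equals true PFS. The type I error stays at 0.0905 and the type II error at 0.0980.

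**The case against.** A reader might infer that stage 1-2 patients have no imaging event at all and can fail only by death. The protocol as a whole does not support this. Section 2.2 and the summary both count new lesions, and after a complete excision with nothing visible, a recurrence can be read as a new lesion. Section 7.1 can itself be read more generously: its Stage 3 phrase sits in the sentence setting a minimum size, not in a list of permitted events, and any tumor above that size could be taken to satisfy a 25% rise from zero. This objection stands as far as it goes. The gap exists only when 7.1 is read literally and alone. But section 2.2 directs readers to chapter 7 for the exact rule, and naming Stage 3 while leaving out two other complete-excision stages does not settle the matter.

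A reader might also infer that many patients are affected. The protocol gives no split of stages 1, 2 and 3, so the number is unknown. The column with no deaths is a worst case, since death from any cause is an event.

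Finally, section 6.1 says "The post-operative MRI brain study should be done within 48 hours of the operation", while section 5.1.3 mentions "the post-operative MRI as obtained shortly before the registration". It is tempting to call these two rival baselines for progression. The documents do not show that: 5.1.3 concerns image fusion for radiotherapy planning, and no text makes that scan a comparator for tumor growth. What remains is that 7.1 names no comparator.

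**Conclusion.** The definitions of the primary endpoint contradict each other, and the wording of 7.1 needs correcting. The omission of new lesions, and of recurrence after stage 1-2, is plain on the face of the text. How much harm it does depends on which definition sites follow.

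If 7.1 is applied literally and alone, false success at a true 3-year PFS of 70% rises from 0.09 to between 0.23 and 0.96 over the assumed shares. Those figures rest on assumed stage shares, an assumed proportion of deaths, no censoring, and no stage 1-2 recurrence being counted at any site. They illustrate the direction and possible size of the bias and do not forecast it. If sites follow 2.2 and the summary, there is no inflation.

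For stage 4-5 the 25% rule has a residual to work from, so only the new-lesion conflict and the unnamed comparator apply there. No size is put on these.

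**What to change.** Reconcile 7.1 with section 2.2 and the summary. State in 7.1 that progression comprises:

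- the appearance of new lesions, in any stage;
- tumor recurrence after any Simpson 1-3 resection;
- a 25% increase in calculated volume where residual tumor exists.

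Say to which of these the 0.065 cc minimum applies. At present it is attached only to the volume increase and to Stage 3 recurrence, and neither 2.2 nor the summary sets a minimum for new lesions, so this is for the sponsor to decide and write down. Name the MRI against which the 25% increase is measured.

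Section 5.1.3 and radiotherapy planning need no change. The cost is wording in 7.1 and on the progression case report form, with no new procedure. N, the type I error and the type II error are unaffected.

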7.2 Progression-free survival

Progression-free survival will be counted from the date of randomization until the date of the first event of either progression or death due to any cause. Patients alive without progressive disease at the time of data analysis will be censored at the time of the most recent follow-up visit.

7.3 Overall survival

Overall survival is counted from the date of randomization. Patients who die are reported as events, irrespective of the cause of death. Patients without the event of interest are censored at the time of most recent follow-up visit

7.4 Adverse events

Side effects (acute and late) of the treatment will be assessed using the International Common Toxicity Criteria (CTC), version 3.0 scoring system. A copy of the CTC can be accessed from the CTEP home page (<http://ctep.info.nih.gov/reporting/ctc.html>). A link to this page is provided on the EORTC web site (<http://www.eortc.be/>). If the location is moved to another site, this link will be updated. Investigators who do not have any access to Internet can contact the EORTC Data Center to receive a copy by mail.

7.5 Evaluation of neurologic function

Short cognitive screening with the *Mini-Mental State Examination* (Ref. 100) will take place at randomisation and then at every scheduled follow-up visit as indicated in chapter 6. This 30-point test includes questions on orientation to time and place, registration, attention, calculations, recall, language, and visual construction (See Appendix F).

8 Statistical considerations

8.1 Statistical design

8.1.1 Sample size

For patients with atypical meningioma (grade II) the trial is designed as two parallel non-randomized phase-II trials with progression-free survival rate at 3-years as primary endpoint.

The trial is therefore stratified in two groups: the patients with Simpson's stage 1-3 resection and patients with Simpson's stage 4-5 resection.

A separate one-stage Fleming design (Ref. 101) will be applied each to the two strata of patients with WHO grade II disease. The criteria for success are respectively to demonstrate that the 3-year progression free survival is superior to 70% for patients with Simpson's stage 1-3 and that it is superior to 50% for patients with Simpson's stage 4-5.

With such a design, a total of 25 patients with Simpson stage 1-3 grade II meningiomas and 39 patients with Simpson stage 4-5 meningiomas **eligible and starting treatment** are needed (total phase II study, 64 patients).

For the grade III meningiomas, given the small numbers expected to enter the trial, the patients will only be followed-up similarly to the grade II meningiomas. No specific statistical design, no decision rule and no sample size are defined for this small group. Only descriptive statistics will be produced. The trial duration will be driven by the phase II study. It is foreseen that 6-13 grade-III patients will be registered during the accrual period of the phase II.

Accrual to the phase II is anticipated to last 3 years.

All patients need to be followed for a minimum of 3 years or until death or progression of the disease. Ineligible patients and those who do not start treatment need to be replaced in the sample.

8.1.1.1 Parameters of the design for WHO grade II and Simpson's stage 1-3

For Simpson stage 1-3 grade II meningiomas,

- ◆ A 3-year PFS rate of 70% is considered too low ($P_0 = 70\%$) to warrant further testing of 60Gy irradiation whereas a 3-year PFS rate of 90% ($P_1=90\%$) would be considered enough to warrant further study of the treatment
- ◆ The type I error rate (α) is 0.09
- ◆ The type II error rate (β) is 0.098
- ◆ With this design, there is therefore 9% risk of considering that the irradiation is sufficiently active if the true progression-free survival rate at 3 years is in fact only 70% and there is 9.8% risk of failing to demonstrate it is sufficiently active, if the true progression-free survival rate at 3 years is 90%
- ◆ The treatment will be considered active enough if for Simpson stage 1-3 grade II meningiomas the lower bound of the 1-sided 90% confidence interval of the 3-year PFS rate estimated by Kaplan-Meier (using log-log transform) is $>70\%$

8.1.1.2 Parameters of the design for WHO grade II and Simpson's stage 4-5

For Simpson stage 4-5 grade II meningiomas,

- ◆ A 3-year PFS rate of 50% is considered too low ($P_0 = 50\%$) to warrant further testing of 70Gy irradiation whereas a 3-year PFS rate of 70% ($P_1=70\%$) would be considered enough to warrant further study of the treatment
- ◆ The type I error rate (α) is 0.10
- ◆ The type II error rate (β) is 0.094
- ◆ With this design, there is therefore 10% risk of considering that the irradiation is sufficiently active if the true progression-free survival rate at 3 years is in fact only 50% and there is 9.4% risk of failing to demonstrate it is sufficiently active, if the true progression-free survival rate at 3 years is 70%
- ◆ The treatment will be considered active enough if for Simpson stage 4-5 grade II meningiomas the lower bound of the 1-sided 90% confidence interval of the 3-year PFS rate estimated by Kaplan-Meier (using log-log transform) is $>50\%$.

8.1.2 Registration and stratification

Patients will be centrally registered but not randomized (for practical details, see chapter on registration procedure).

At registration, the patients will be grouped according to the WHO tumor grade and the resection's Simpson's stage as:

- ◆ WHO grade II, Simpson's stage 1-3
- ◆ WHO grade II, Simpson's stage 4-5
- ◆ WHO grade III, Simpson's stage 1-3
- ◆ WHO grade III, Simpson's stage 4-5

8.2 Statistical analysis plan

8.2.1 Primary and secondary endpoints

8.2.1.1 Progression-free survival (primary endpoint)

Progression-free survival will be counted from the date of registration until the date of the first event of either progression or death due to any cause. Patients alive without progressive disease at the time of data analysis will be censored at the time of the most recent follow-up visit.

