6.3 During the follow-up

6.3.1 The first follow-up

The first follow-up will be 6 weeks after the last irradiation and will focus on possible acute irradiation toxicity (see table in chapter 6.4). The following evaluation will be performed:

- ◆ Clinical examination, performance status evaluation (WHO-ECOG), interim medical history.
- ◆ Concomitant medications
- ◆ Mini-Mental Status Examination (MMSE, see Appendix F)
- ◆ Acute adverse events scoring according to the National Cancer Institute Common Terminology Criteria for Adverse Events (CTCAE) v.3.0 (<http://ctep.cancer.gov/forms/CTCAEv3.pdf>) grading system.
- ◆ No MRI is requested.

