6.3.2 The further follow-up

The next follow-up will be at 6 months after entry on study, then at month 12 and then annually.

Until disease progression, every scheduled follow-up visit includes the following evaluation (see table in chapter 6.4).:

- ◆ Clinical examination, performance status evaluation (WHO-ECOG), interim medical history.
- ◆ Concomitant medications
- ◆ Mini-Mental Status Examination (MMSE, see Appendix F)
- ◆ Late adverse events scoring according to the National Cancer Institute Common Terminology Criteria for Adverse Events (CTCAE) v.3.0 (<http://ctep.cancer.gov/forms/CTCAEv3.pdf>) grading system.
- ◆ Contrast enhanced (gadolinium) MRI (T1, T1 Gado, T2) with slice thickness of 3-5 mm.

After disease progression, the patients will only be followed-up for survival.

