8.2.1.2 Overall survival (secondary endpoint)

Overall survival is counted from the date of registration. Patients who die are reported as events, irrespective of the cause of death. Patients without the event of interest are censored at the time of most recent follow-up visit.

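### PFS is censored at the last visit rather than the last MRI, which can bias the 3-year rate upward where a patient is seen without the scheduled scan

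*Protocol*

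**What the plan says.** Section 8.2.1.1 fixes the censoring date for PFS: "Patients alive without progressive disease at the time of data analysis will be censored at the time of the most recent follow-up visit". Section 7.2 has the same rule. The protocol summary (Criteria for evaluation) covers PFS and overall survival together: "the patients not having experienced the event(s) of interest are censored at the date of most recent follow-up".

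The summary defines progression "as demonstrated by an MRI showing either appearance of new lesions or increased in tumor size by 25% using 3 dimensions". Section 7.1 adds the measurement rule, a volume computed from three diameters.

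The schedule in 6.3.2 reads: "The next follow-up will be at 6 months after entry on study, then at month 12 and then annually". The same section puts a contrast-enhanced MRI among the evaluations at each of these visits until progression, and the table in 6.4 agrees. The one scheduled follow-up visit without a scan is the visit 6 weeks after irradiation (6.3.1): "No MRI is requested".

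For overall survival, 8.2.1.2 (and 7.3) says: "Patients without the event of interest are censored at the time of most recent follow-up visit". Section 6.3.2 adds: "After disease progression, the patients will only be followed-up for survival".

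**The concern.** The censoring date comes from a contact that need not be able to detect the event. Take a patient scanned free of progression at month 24 and seen at month 36 without a scan, with no later contact. Under the rule this patient stays in the risk set through month 36 as progression-free, although nothing is known about the tumour after month 24. A visit without a scan cannot register a progression, so the error goes only one way, toward a higher 3-year rate. Scans are yearly after month 12, so one missed scan leaves 24 months unobserved.

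The 3-year rate carries the success decision in each grade II stratum, and one patient can settle it (see the working). The rule is written into the protocol for the primary endpoint itself, so an analysis plan that follows the protocol inherits it.

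**Working it through.** **Inputs from the protocol.** 25 patients with P0 = 0.70 and P1 = 0.90 (Simpson 1-3); 39 patients with P0 = 0.50 and P1 = 0.70 (Simpson 4-5) (8.1.1 to 8.1.1.2). Success means that the one-sided 90% log-log lower bound of the Kaplan-Meier 3-year rate, with Greenwood variance, exceeds P0 (8.2.3.2). Visits are at months 6, 12, 24, 36 and yearly (6.3.2). Minimum follow-up is 3 years and accrual is expected to take 3 years (8.1.1).

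**Assumptions.** The share m of attended visits without an MRI is not given; 0 to 30% is shown. PFS is exponential, there are no deaths, follow-up is uniform over 36 to 72 months, visits fall on schedule, and scans are missing at random.

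**Step 1: reproduce the design.** Exact binomial:
- P(X ≥ 21 | 25, 0.70) = 0.0905 and P(X ≤ 20 | 25, 0.90) = 0.0980; stated 0.09 and 0.098.
- P(X ≥ 24 | 39, 0.50) = 0.0998 and P(X ≤ 23 | 39, 0.70) = 0.0944; stated 0.10 and 0.094.

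Without censoring, S = r/n and the lower bound is exp{−exp[log(−log S) + 1.2816 × se]}, with se = √((1−S)/(nS)) / |log S|:
- 20/25 gives 0.673 (fail); 21/25 gives 0.718 (success).
- 23/39 gives 0.482 (fail); 24/39 gives 0.508 (success).

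The bound therefore has the same cut-offs as the binomial design, and one patient separates failure from success.

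**Step 2: size of the shift in a simple case.** Suppose every patient's last visit is month 36 and a share m lacks only that scan. The upward shift is m × (P^(2/3) − P), where P is the true 3-year rate.
- P = 0.70: 0.7884 − 0.70 = 0.0884; 0.9 points at m = 10%, 2.7 at 30%.
- P = 0.50: 0.6300 − 0.50 = 0.1300; 1.3 points at 10%, 3.9 at 30%.
- P = 0.90: 0.9322 − 0.90 = 0.0322; 0.3 points at 10%, 1.0 at 30%.

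**Step 3: isolate the censoring rule.** The shift in Step 2 mixes the missed scan with the rule. To separate them, 4,000 trials per setting were simulated and both rules were applied to the same data, with scans missing at any attended visit. Each cell gives last visit / last MRI.

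| m | n = 25, true 0.70: mean KM | type I error | n = 39, true 0.50: mean KM | type I error |
|---|---|---|---|---|
| 0 | 0.698 / 0.698 | 0.089 / 0.089 | 0.499 / 0.499 | 0.095 / 0.095 |
| 10% | 0.710 / 0.706 | 0.113 / 0.110 | 0.515 / 0.509 | 0.136 / 0.119 |
| 20% | 0.724 / 0.715 | 0.139 / 0.124 | 0.534 / 0.520 | 0.204 / 0.142 |
| 30% | 0.737 / 0.719 | 0.170 / 0.124 | 0.557 / 0.530 | 0.289 / 0.163 |

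Simulation error is about 0.005 on a rejection rate near 0.10 (√(0.1 × 0.9/4000) = 0.0047). A second simulation gave about 0.10 under both rules (n = 25) and 0.135 / 0.118 (n = 39) at 10%, and 0.165 / 0.121 and 0.288 / 0.164 at 30%.

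**Step 4: the 6-week visit.** It falls before the first scheduled scan at month 6. Moving a patient last seen there back to registration changes no risk set at a progression time, so the 3-year estimate is unchanged, apart from early deaths or unscheduled scans.

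**The case against.** The strongest reply is that the protocol already ties scan to visit. Sections 6.3.2 and 6.4 require an MRI at every scheduled visit from month 6 until progression, so under compliance the two dates coincide and the rules do not differ. That stands. A reader might infer from the wording of 8.2.1.1 that the 3-year rate is biased upward as a matter of course. The documents do not support this: the bias needs scans missed at attended visits, and no rate is given for them.

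A reader might also point to the MRI-free 6-week visit as a built-in source of bias. Step 4 shows it is harmless for the 3-year rate.

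A third tempting step is to charge the whole effect of missed scans to the rule. If 10% of third-year progressors lack the month-36 scan and all count as 3-year successes, the binomial false-success risk rises from 0.090 to 0.107 and from 0.100 to 0.131. But many of these patients would be scanned at month 48 and their progression dated there, which is a 3-year success under either rule. Simulating that case (6,000 trials, only the month-36 scan missed), last visit versus last MRI gives 0.107 versus 0.106 (n = 25) and 0.127 versus 0.115 (n = 39) at 10%, and 0.139 versus 0.126 and 0.210 versus 0.163 at 30%. The rule accounts for only part of the rise, and for almost none of it in the smaller stratum at 10%.

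What the reply does not meet is that a censoring rule has to cover imperfect compliance, and this one settles such cases in the favourable direction.

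On overall survival, one might read the visit-based rule as a serious bias. It is not shown to be: 6.4 makes survival status mandatory at every follow-up, also after progression, and the endpoint carries no decision rule (8.2.3.2).

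**Conclusion.** The point holds conditionally. The rule is unbiased if the scan schedule is kept, and biased toward success where patients are seen without a scan. The rule's own contribution, from the table in the working, is:
- none with complete scans;
- at 10% missed, 0.4 to 0.6 points on the 3-year estimate, no clear change in type I error for 25 patients, and 0.136 − 0.119 = 0.017 for 39;
- at 30% missed, 0.170 − 0.124 = 0.046 and 0.289 − 0.163 = 0.126.

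The Simpson 4-5 stratum is the more exposed, and its exact design error of 0.0998 leaves no room below the 10% limit. These sizes rest on the stated assumptions, above all on the missed-scan share. The overall survival wording is a minor matter: a patient known to be alive from a contact other than a visit would be censored too early.

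**What to change.** In the protocol summary, 7.2 and 8.2.1.1, censor patients alive without progression at the date of the last MRI showing no progression, or at registration if there is no MRI after it. As a minor companion change in the summary, 7.3 and 8.2.1.2, censor overall survival at the date last known alive, whatever the type of contact.

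This is a change of wording with no new procedure. The case report forms are not part of the documents, so it should be confirmed that they record each scan date.

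The cost is slightly fewer patients at risk at 3 years and a slightly wider interval. In the same simulations, power under last-MRI versus last-visit censoring was 0.913 versus 0.916 (n = 25) and 0.900 versus 0.920 (n = 39) at 10% missed scans, and 0.885 versus 0.939 and 0.925 versus 0.970 at 30%. Part of the power given up is the same upward bias. The change does not remove the bias entirely, because a progression missed at one visit is dated at the next scan: for 39 patients, type I error still reaches 0.119 at 10% missed and 0.163 at 30%. Complete scanning is what removes the rest.
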